7.1.2. Temporary Discontinuation of Study Intervention

Temporary withholding of study intervention is required if the participant meets any of the following infection-related criteria during the study:

- Serious or opportunistic infections, as defined in Section 5.2. Study intervention is to be withheld until resolution of all acute clinical signs and symptoms, and completion of all appropriate anti-infective treatment.
- HBV DNA results that are reported as positive, or as detecting HBV DNA, but HBV DNA is below the level of quantification. In this situation, the sponsor's designated medical monitor should be contacted regarding the participant's status. HBV DNA testing is to be repeated as soon as is feasible. If HBV DNA is confirmed as positive, the participant must be permanently discontinued from study intervention as described in Section 7.1.
- If a participant <18 years of age loses a clinically significant amount of weight (below 40 kg), the investigator should assess rationale for weight loss and use clinical judgment to determine if the participant should temporarily discontinue the treatment.

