7.1. Discontinuation of Study Intervention

When necessary, a participant may be permanently discontinued from study intervention. If so, the participant will remain in the study to complete procedures for an early discontinuation visit and post-treatment follow-up, if applicable, as shown in the SoA.

A participant should be permanently discontinued from study intervention if

- the participant becomes pregnant during the study
- in the opinion of the investigator, the participant should permanently discontinue the study intervention for safety reasons
- the participant develops a malignancy, except for successfully treated basal or squamous cell skin carcinoma
- the participant tests positive for HBV DNA (see Section 8.2.3)
- the participant tests positive for HCV RNA (Section 8.2.4)
- if the participant experiences a hepatic event or liver test abnormality as specified in the liver chemistry stopping criteria (see Section 7.1.1)
- the participant develops HIV infection
- the participant requires rescue medication treatment for symptoms of AD in the treatment period
- the participant develops any infection that is opportunistic, such as active tuberculosis and other infections whose nature or course may suggest an immuno-compromised status, and
- the participant has an AE or an SAE or a clinically significant change in a laboratory value that, in the opinion of the investigator, merits discontinuation of study intervention and appropriate measures being taken.

Hepatitis

- prior to discontinuation of any immunomodulatory and/or immunosuppressive therapy due to hepatitis, including study intervention, the participant is to be referred to, evaluated, and managed by a specialist physician with expertise in evaluation and management of viral hepatitis.
- the timing of discontinuation from study intervention relative to the initiation of any antiviral treatment for hepatitis is to be based on the recommendation of the consulting specialist physician, in conjunction with the investigator, and aligned with medical guidelines and standard of care.

Hypersensitivity

- if the investigator determines that a systemic hypersensitivity reaction has occurred related to study intervention administration, the participant may be permanently discontinued from the study intervention, and the sponsor's designated medical monitor

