7.1.1. Liver Chemistry Stopping Criteria

The study drug should be interrupted and close hepatic monitoring initiated (see Section 8.2.2) if 1 or more of these conditions occur:

Elevation ^a	Exception ^a
ALT or AST >8x ULN	
ALT or AST >5x ULN for more than 2 weeks	
ALT or AST >3x ULN and either TBL >2x ULN or INR >1.5	For participants with Gilbert's syndrome: If baseline direct bilirubin is >0.5 mg/dL, then doubling of direct bilirubin should be used for drug interruption decisions rather than TBL >2x ULN.
ALT or AST >3x ULN with the appearance of fatigue, nausea, vomiting, right upper quadrant pain or tenderness, fever, and/or rash	
ALP >3x ULN, when the source of increased ALP is the liver	
ALP >2.5x ULN and TBL > 2x ULN	For participants with Gilbert's syndrome: If baseline direct bilirubin is >0.5 mg/dL, then doubling of direct bilirubin should be used for drug interruption decisions rather than TBL >2x ULN.
ALP >2.5x ULN with the appearance of fatigue, nausea, vomiting, right upper quadrant pain or tenderness, fever, and rash	
Source: FDA Guidance for Industry: Drug-Induced Liver Injury: Premarketing Clinical Evaluation, July 2009 and other consensus guidelines, with minor modifications.	

Abbreviations: ALP = alkaline phosphatase; ALT = alanine aminotransferase; AST = aspartate aminotransferase; INR = international normalized ratio; TBL = total bilirubin; ULN = upper limit of normal.

^a All ULN values should be age adjusted (AAULN) for participants <18 years of age.

Resumption of the study intervention can be considered only in consultation with the Lilly-designated medical monitor and only if liver test results return to baseline and if a self-limiting non-drug etiology is identified. Otherwise, study intervention should be discontinued.

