7.3. Lost to Follow-up

A participant will be considered lost to follow-up if he or she repeatedly fails to return for scheduled visits and is unable to be contacted by the study site. Site personnel or designee are expected to make diligent attempts to contact participants who fail to return for a scheduled visit or were otherwise unable to be followed up by the site.

8. Study Assessments and Procedures

- Study procedures and their timing are summarized in the SoA.
- Immediate safety concerns should be discussed with the sponsor immediately upon occurrence or awareness to determine if the participant should continue or discontinue study intervention.
- Adherence to the study design requirements, including those specified in the SoA, is essential and required for study conduct.
- All screening evaluations must be completed and reviewed to confirm that potential participants meet all eligibility criteria. The investigator will maintain a screening log to record details of all participants screened and to confirm eligibility or record reasons for screening failure, as applicable.

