8.3.3. Adverse Events of Special Interest

The following TEAEs will be designated AE of special interest (AESI):

- conjunctivitis
- herpes infection or zoster, and
- parasitic infection or an infection-related to an intracellular pathogen.

If these AESIs are reported, sites will be prompted to collect additional data. Participant records must include any follow-up information regarding these AESI. Study intervention should be discontinued if an AE is deemed persistent and if continuation of study intervention would not be in the best interest of the participant. Discuss discontinuation of study intervention with the sponsor or designee prior to implementation.

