8.3.3.1. Infections, Including Serious Infections and Opportunistic Infections

Completion of the Infection CRF page is required for each infection reported as an AE or SAE. The sponsor will identify infections considered to be opportunistic based on the article by Winthrop et al. (2015) (Section 10.9, Appendix 9).

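### Protocol 7.1.2 places opportunistic infections under a temporary hold with no pointer to the permanent stop in 7.1, so the restart rule is unclear

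*Protocol*

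**What the plan says.** Protocol 7.1 lists the events for which a participant should permanently stop study drug. One is that "the participant develops any infection that is opportunistic, such as active tuberculosis and other infections whose nature or course may suggest an immuno-compromised status".

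Protocol 7.1.2 lists infection-related events for which a temporary hold is required. Its first bullet reads "Serious or opportunistic infections, as defined in Section 5.2. Study intervention is to be withheld until resolution of all acute clinical signs and symptoms", and it adds completion of all appropriate anti-infective treatment as a second condition for ending the hold. The bullet takes its definition from Section 5.2, where exclusion 24b refers to Appendix 9. Appendix 9 gives examples of infections that may count as opportunistic, and tuberculosis is among them.

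The next bullet of 7.1.2, on detectable hepatitis B DNA, goes one step further: "If HBV DNA is confirmed as positive, the participant must be permanently discontinued from study intervention as described in Section 7.1". The infection bullet has no such step.

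**The concern.** A stopping rule should give one answer for each event. Here one infection, tuberculosis, meets a rule that ends treatment for good and a rule whose heading and end condition suggest a pause. A site that opens 7.1.2 alone finds the conditions under which the hold ends and nothing to say that an opportunistic infection should not be followed by further dosing. A site that opens 7.1 finds a permanent stop.

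At stake is the safety of the individual participant at the point of restart. This is a multi-site study (SAP 5.5) that includes adolescents, allows dosing at home and has no data monitoring committee (Protocol 1.1), so the written rule carries much of the weight.

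**Working it through.** No arithmetic decides this point. It is a comparison of texts.

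**Step 1: do the two rules cover the same event?** Yes, for at least one infection. 7.1 names active tuberculosis, and 7.1.2 reaches tuberculosis through exclusion 24b and Appendix 9, which lists it without a qualifier. In 7.1 the words about an immunocompromised status describe the other infections, so they do not narrow the reference to any opportunistic infection.

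**Step 2: set the rules side by side.**

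| | 7.1 | 7.1.2, first bullet |
|---|---|---|
| Force | *should* | *required* |
| Trigger | any opportunistic infection | serious or opportunistic infection |
| Action | permanent stop | hold |
| End of action | none | resolution and completed treatment |
| Pointer to the other rule | none | none |

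**Step 3: does the wording rank them?** No. The permanent rule has the weaker verb. 7.1.2 is a subsection of 7.1, which fits either reading: a first step under the general rule, or a specific exception to it.

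**Step 4: how do neighbouring rules handle restart?** The hepatitis B bullet sends confirmed cases to 7.1. The liver rule in 7.1.1 says "Resumption of the study intervention can be considered only in consultation with the Lilly-designated medical monitor", adds conditions, and otherwise calls for discontinuation. Only the infection bullet leaves the step after the hold unstated.

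**Step 5: what do the entry criteria imply?** Exclusion 20 bars people with a history of invasive opportunistic infection, tuberculosis among the examples, even if it has resolved. Resolved tuberculosis would therefore keep a person out at entry, while resolved and treated tuberculosis meets the condition for ending a 7.1.2 hold. The permanent stop in 7.1 is the reading consistent with exclusion 20.

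**Step 6: does any other text settle it?**
- Protocol 8.3.3 covers adverse events of special interest. These include herpes infection or zoster and infections with an intracellular pathogen, a group that would ordinarily take in tuberculosis. Its test for stopping, which turns on what is best for the participant, reads "Study intervention should be discontinued if an AE is deemed persistent and if continuation of study intervention would not be in the best interest". It also asks sites to consult the sponsor before they stop drug. Both provisions concern stopping, not restart after a hold.
- Protocol 8.3.3.1 says that the sponsor identifies which infections are opportunistic. It does not say what follows for dosing.
- The opening bullets of Protocol 8 say "Immediate safety concerns should be discussed with the sponsor immediately upon occurrence or awareness", in order to decide whether treatment continues. They do not rank the two rules.
- The SAP does not address the point.

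**The case against.** The strongest reply is that the two rules can both be obeyed. The site holds drug at once under 7.1.2, the sponsor identifies the infection as opportunistic, and the participant then stops for good under 7.1. A permanent stop never breaches a hold. The until-resolution condition still has work to do, because serious infections that are not opportunistic fall under 7.1.2 and not under the infection bullet of 7.1. This stands. A reader might infer that the sections flatly contradict each other, or that 7.1.2 authorises restart after tuberculosis. The text supports neither. What remains is that no sentence states the hold-then-stop sequence for this bullet, although one does for hepatitis B.

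Re-dosing after tuberculosis within the study also looks remote. A site would have to overlook its being named in 7.1 and pass the investigator-judgement bullets there. Anti-infective treatment would have to finish before the last scheduled dose at Week 20 or 22 (Protocol 6.1), and 6.8.2 prohibits chronic systemic anti-infectives. This stands too, and it limits the practical risk. Continued access (Protocol 6.6) can extend dosing, but its rules are in an addendum that is not among these documents.

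A reader might further infer that every Appendix 9 infection meets two conflicting rules. That goes too far. Confirmed hepatitis B DNA is already routed to a permanent stop, as is hepatitis C RNA (7.1 and 8.2.4). Nor does 7.1 clearly force a permanent stop for uncomplicated zoster, since Appendix 9 lists what may be considered opportunistic.

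**Conclusion.** The point holds in a limited form. For an opportunistic infection, 7.1 gives a permanent stop, 7.1.2 gives a hold with an end, and no text joins the two. The defect is an unclear restart rule. Dosing stops under either section during the acute illness, and contact with the sponsor is already expected, so unilateral restart is unlikely. But the sponsor's monitor would have the same two texts to work from.

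No event probability is attached. The documents give no rate, and Protocol 2.3 reports no opportunistic infections in its account of the three Phase 3 trials. An assumed rate would have no support in these documents.

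A reader might infer that the ambiguity threatens the primary result, because a permanent stop before Week 16 takes a participant out of the primary estimand population while a hold does not. The documents do not support a material effect. With 120 participants and the anticipated 50% response (60/120), removing one gives 60/119 = 50.4% or 59/119 = 49.6%, a shift of about 0.4 percentage points. The plan's own 90% interval at that rate runs from 42.6% to 57.4%.

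The conclusion rests on the wording alone and on no numerical assumption. A correction is worthwhile because this is a safety rule and the repair is small.

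**What to change.** Leave 7.1 as it is. Narrowing its permanent stop to infections that suggest immunocompromise would change policy, not reconcile the sections.

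In the first bullet of 7.1.2, keep the immediate hold for all serious or suspected opportunistic infections, and add:

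> *An infection identified as opportunistic (Section 8.3.3.1) leads to permanent discontinuation under Section 7.1; after a serious infection that is not opportunistic, dosing may resume once the infection has resolved and its treatment is complete, in consultation with the medical monitor.*

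If the sponsor wants to allow restart after a particular Appendix 9 infection, such as uncomplicated herpes zoster, it should list that exception by name in 7.1.

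The cost is one sentence in the next amendment, with the ethics approval that any amendment needs (Protocol 10.1.1), and a contact with the medical monitor before any restart. That contact also ensures that the sponsor's classification reaches the site before dosing resumes. No visits, samples or data fields are added.

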7.2. Participant Discontinuation/Withdrawal from the Study

Discontinuation is expected to be uncommon.

A participant may withdraw from the study

- at any time at the participant's own request
- at the request of the participant's designee (for example, parents or legal guardian)
- at the discretion of the investigator for safety, behavioral, compliance, or administrative reasons
- if enrolled in any other clinical study involving an investigational product, or enrolled in any other type of medical research judged not to be scientifically or medically compatible with this study, and
- if the participant, for any reason, requires rescue medication or treatment with a therapeutic agent that is prohibited by the protocol and has been demonstrated to be effective for treatment of the study indication. In this case, discontinuation from the study occurs prior to introduction of the new agent.

At the time of discontinuing from the study, the participant will complete procedures for an early discontinuation visit and post-treatment follow-up, if applicable, as shown in the SoA. If the participant has not already discontinued the study intervention, the participant will be permanently discontinued from the study intervention at the time of the decision to discontinue the study.

If the participant withdraws consent for disclosure of future information, the sponsor may retain and continue to use any data collected before such a withdrawal of consent. If a participant withdraws from the study, the participant may request destruction of any samples taken and not tested, and the investigator must document this in the site study records.

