6.8.5. Rescue Medicine for Atopic Dermatitis

To be consistent with real world practice, defined topical medications are allowed in this study (see Section 6.8.4). However, rescue therapies may be needed if the participant experiences intolerable clinical worsening of symptoms. Escalation to high potency topical TCS, topical JAK inhibitors, phototherapy and/or systemic medications (including but not limited to corticosteroids, immunosuppressants, biologics, small molecules, etc.) for the treatment of AD should only occur if participants do not respond adequately after at least 7 days of low/mid potency TCS, TCI and/or topical PDE4 inhibitors. Any use of topical JAKs, phototherapy, and/or systemic medications will be considered rescue therapy. Use of high-potency TCS for more than 10 days is also considered rescue therapy. Participants that receive Rescue therapy must be discontinued from the study. (see Section 7.1).

All rescue medication must be recorded in the CRF.

7. Discontinuation of Study Intervention and Participant Discontinuation/Withdrawal

Discontinuation of specific sites or of the study as a whole are handled as part of Appendix 1.

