participants with moderate-to-severe AD who have been previously treated with dupilumab if all participants adhered to treatment?

This estimand is described by the following attributes:

- A. Population: Treatment Period II population as described in Section 5.1.1.
- B. Endpoint: apply to all secondary endpoints at Week 24.
- C. Intercurrent events (ICEs): One ICE, permanent treatment discontinuation, is considered by this estimand as follows:
  - a. For participants who discontinue treatment after Week 16, a hypothetical strategy will be used to estimate what the treatment effect would have been if all subjects continued with treatment. Therefore, a hypothetical strategy is used for this type of ICE.
- D. Population-level summary: Population-level summary: percentage of successful responses or means at Week 24.

Because participants who initiate rescue medication are required to discontinue from the study and hence permanently discontinue study treatment, the supportive estimands for the primary and secondary endpoints only consider permanent treatment discontinuation as an ICE.

Analytical details on how missing data including those as a result of intercurrent events will be handled can be found in Section 5.4. The following table (Table KGBO.5.2) summarizes the analytical strategies that will be conducted on the intercurrent events for the five estimands.

		Analysis Stra Perman Disco	Missing Data		
Estimand	Population	Due to lack of efficacy	Due to any other reasons, including initiation of rescue medication	Imputation Method	
Primary Estimand for the Primary Endpoint and Secondary Endpoints	ITT Population who remained on treatment	Not applicable	Not applicable	Primary analysis: as observed	
Supportive Estimand for the Primary Endpoint and Secondary	ITT Population	Composite: Set to baseline	Hypothetical: Set to missing	MCMC-MI	

Endpoints at Week 16 (Hybrid)				
Supportive Estimand for the Primary Endpoint and Secondary Endpoints at Week 16 (Hypothetical)	ITT Population	Hypothetical: Set to missing	Hypothetical: Set to missing	LOCF
Supportive Estimand for Secondary Endpoints at Week 24 (Hybrid)	Treatment Period II Population	Composite: Set to baseline	Hypothetical: Set to missing	MCMC-MI
Supportive Estimand for Secondary Endpoints at Week 24 (Hypothetical)	Treatment Period II Population	Hypothetical: Set to missing	Hypothetical: Set to missing	LOCF

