### 5.4.2. Last Observation Carried Forward

In this analysis, all missing values will be imputed using last observation carried forward (LOCF). Baseline values will be used for imputation if there is no postbaseline observation.

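### EASI values recorded after high-potency TCS has become rescue, but on or before discontinuation, have no rule in the SAP, and the protocol's statements on rescue and discontinuation do not agree

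*Protocol*

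**What the plan says.** Protocol Sections 6.8.4 and 6.8.5 tie a mandatory consequence to receipt of rescue: "Participants that receive Rescue therapy must be discontinued from the study". Both refer to Section 7.1. One kind of rescue is defined by duration: "Use of high-potency TCS for more than 10 days is also considered rescue therapy". Up to 10 days, the same treatment is permitted (Section 6.8.1).

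Section 7.1 lists, among the reasons for permanently stopping study intervention, that "the participant requires rescue medication treatment for symptoms of AD in the treatment period". After stopping, "the participant will remain in the study to complete procedures for an early discontinuation visit and post-treatment follow-up".

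Section 7.2 places the need for rescue in a list of reasons for which a participant may withdraw, and adds: "In this case, discontinuation from the study occurs prior to introduction of the new agent". If study intervention has not already stopped, 7.2 dates its end at the decision to leave the study.

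The SAP builds on this. Section 5.2.1 restricts the primary estimand to participants still on treatment at Week 16 and says no intercurrent event can arise, because rescue users are discontinued. Protocol Section 9.3.2 says the same and includes all observed data. SAP Section 5.2.4 states that "the supportive estimands for the primary and secondary endpoints only consider permanent treatment discontinuation as an ICE". Table KGBO.5.2 sets data to missing for discontinuation for reasons other than lack of efficacy, rescue included. LOCF (5.4.2) then fills every missing value under the hypothetical estimands, and MCMC-MI (5.4.3) is used under the hybrid estimands. SAP Appendix 1 defines rescue by drug codes and by more than 10 days of high-potency TCS, but derives no rescue date.

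**The concern.** The absence of intercurrent events in the primary estimand, and the use of treatment discontinuation as the only one in the supportive estimands, both need rescue and discontinuation to happen together. For high-potency TCS they cannot be guaranteed to, because a permitted treatment turns into rescue through continued use. Between crossing the threshold and stopping study intervention, an EASI can be recorded that the estimands intend to be free of rescue but that no SAP rule removes. At stake is whether the reported EASI-75 rate answers the stated question, in the primary analysis as well as the supportive ones.

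**Working it through.** **1. The protocol statements side by side**

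| Section | Trigger | Obligation | What stops | When |
|---|---|---|---|---|
| 6.8.4, 6.8.5 | rescue received | must | the study | after receipt |
| 7.1 | rescue required | should | study intervention; ED visit and follow-up remain | not stated |
| 7.2 | rescue required | may | the study, and study intervention with it | before the agent is introduced |

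**2. Can the 7.2 timing be met?** For topical JAK inhibitors, phototherapy and systemic agents it can, although it then conflicts with the receipt wording in 6.8.5. For high-potency TCS it cannot. Use is permitted through day 10 and is rescue from day 11, so the agent has been in use for 10 days when it becomes rescue. Stopping a participant on day 10 would still not precede introduction. If the staged rule is followed (at least 7 days of low- or mid-potency treatment first), the threshold is reached no earlier than 7 + 11 = day 18 after topical treatment starts.

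**3. Can the threshold be crossed unnoticed before an EASI?** The Schedule of Activities has EASI at Weeks 0, 2, 4, 8, 16, 24 and ED, with gaps of 14, 14, 28, 56 and 56 days. Week 12 is a telephone visit: diary and concomitant medication are reviewed, but EASI is not scored. From Week 12 to Week 16 is 28 days, more than the 11 needed. A course begun after the Week 12 call, or not yet past day 10 at that call, can be first found excessive at Week 16, with the participant still on study treatment and EASI scored that day.

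**4. Where such an EASI goes under the SAP**

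| EASI recorded past the threshold | As observed, Week 16 | LOCF | MCMC-MI |
|---|---|---|---|
| Scheduled visit before Week 16, before discontinuation | not a Week 16 value | can be carried to Week 16 | used in the imputation |
| ED visit on the day of the decision | outside the population if before Week 16 | no rule; may be carried | no rule; may be used |
| Week 16 visit where excess use is first found | counted | not missing, so kept | not missing, so kept |
| ED visit clearly after discontinuation | outside the population if before Week 16 | set to missing | set to missing (to baseline if for lack of efficacy) |

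The first three rows contain the gap. The last is already handled.

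**5. Size.** The plan's own reference figure first. The Wilson 90% interval with p = 0.50, n = 120, z = 1.645 has half-width

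z·√[p(1−p)/n + z²/(4n²)] / (1 + z²/n) = 7.4 points,

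giving 42.6% to 57.4%, as in SAP Section 4.2. The other four rows of that table also reproduce.

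From 60 responders in 120, suppose k participants are counted as responders only because of an EASI past the threshold. Each adds 1/120 = 0.83 points.

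| k (assumed) | Rate | 90% CI |
|---|---|---|
| 1 | 61/120 = 50.8% | 43.4–58.2 |
| 3 | 63/120 = 52.5% | 45.0–59.9 |
| 6 | 66/120 = 55.0% | 47.5–62.3 |

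The table converts counts to points; it does not predict k. In the as-observed analysis, exclusion also shrinks the denominator. Removing one such responder takes 60/120 = 50.0% to 59/119 = 49.6%. Removing one such non-responder gives 60/119 = 50.4%.

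**The case against.** The strongest reply is that the SAP already deals with rescue. Table KGBO.5.2 names it among the discontinuation reasons for which data are set to missing, and 7.2 dates the end of study intervention at the decision to leave. A reader might infer that LOCF generally carries forward the ED-visit EASI of rescued participants. The documents do not support that: an ED value clearly after the decision date should be missing before LOCF is applied. This part of the reply stands. It leaves the same-day ED value, the scheduled visit past the threshold, and the Week 16 visit.

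A second reply is that the protocol sections are closer than they look. Sections 7.1 and 7.2 lead to largely the same procedures: study drug stopped, ED visit, follow-up if applicable. The permissive wording in 7.2 introduces a general list. This also stands, so a reading of three opposed rules would be too strong. The differences in obligation and timing remain.

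Third, low- and mid-potency topicals and up to 10 days of high-potency TCS are permitted by design, so EASI under topical treatment is expected in the results. True, but the plan itself draws the line at 10 days and rests its estimands on nobody being past it.

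Fourth, LOCF and MCMC-MI serve supportive estimands in a descriptive study, and 7.2 expects discontinuation to be uncommon. This limits the weight of the point. It does not remove the Week 16 route, which reaches the primary analysis.

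**Conclusion.** The point holds in a limited form. The protocol sections disagree on obligation and timing, and the 7.2 timing cannot apply to high-potency TCS. As a result, the SAP does not cover an EASI recorded after the rescue threshold and on or before discontinuation. Followed literally, the plan keeps such a value in the as-observed Week 16, LOCF and MCMC-MI results as if it were free of rescue.

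The size cannot be estimated, because the documents give neither a rescue rate nor a response rate past the threshold. A reader might supply them. If 5–10% of 120 reach rescue this way and 25–50% of those meet EASI-75, the result is 6 × 0.25/120 = 1.25 points to 12 × 0.50/120 = 5 points. Those rates are not in the documents. The sum also treats every such participant as otherwise a non-responder, with no earlier response to carry forward. Only the conversion of 0.83 points per changed participant, at N = 120, can be relied on. The conclusion also assumes that excess use can go unnoticed until a visit, which the schedule permits but does not make certain.

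**What to change.** **Protocol.** The sponsor should reconcile Sections 6.8.4, 6.8.5, 7.1 and 7.2 on what is discontinued, whether it is obligatory, and when. No view is taken here on which clinical rule is right.

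**SAP Sections 5.2 and 5.4, with Appendix 1.**
- Define the date on which rescue status is reached, derived from the diary and CRF. State whether the 10 days of high-potency TCS are consecutive or cumulative, and how an EASI on the threshold date or on the same day as discontinuation is classified.
- Set efficacy values recorded after rescue status is reached to missing before LOCF and MCMC-MI. This extends the hypothetical strategy already used for discontinuation.
- Exclude those values from the as-observed Week 16 analysis, so that it matches the stated estimand.

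**Cost.** A protocol clarification and a short SAP addition. TCS use is already recorded daily from Visit 2, and Appendix 1 already identifies high-potency products by code, but the date cannot be derived until the 10-day count is defined. Slightly fewer observed values will remain and the reported rate may be slightly lower. In the as-observed analysis it can move either way, depending on whether the excluded values were responses.
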